### 3 OBJECTIVES AND ENDPOINTS

Objectives	Endpoints
Primary	Primary
To evaluate the efficacy in terms of clinical status following treatment with GT0918 compared to placebo	
Percentage of subjects who do not experience any of the following events due to all causes by Day 28:
 
 
• Hospitalization for <math>\geq</math> 24 hours
 
• Supplemental oxygen for <math>\geq</math> 24 hours in response to <math>\text{SpO}_2 \leq 93\%</math>
 
• Death
 

Secondary	Secondary
To evaluate the clinical efficacy of GT0918 compared to placebo using the NIAID 8- point scoring scale	
Percentage of subjects achieving each clinical status on Days 7, 14 and 28 as defined below based on The National Institute of Allergy and Infectious Diseases (NIAID) 8- point scoring scale:
 
 
1 Death
 
2 Hospitalized, on invasive mechanical ventilation or extracorporeal membrane oxygenation (ECMO)
 
3 Hospitalized, on non-invasive ventilation or high flow oxygen devices
 
4 Hospitalized, requiring supplemental oxygen
 
5 Hospitalized, not requiring supplemental oxygen - requiring ongoing medical care (COVID-19-related or otherwise)
 
6 Hospitalized, not requiring supplemental oxygen - no longer requires ongoing medical care
 
7 Not hospitalized, limitation on activities and/or requiring home oxygen
 
8 Not hospitalized, no limitations on activities
 

To evaluate the clinical efficacy of GT0918 compared to placebo based on clinical status	
 
Proportion of subjects with all-cause hospitalization (defined as <math>\geq 24</math> hours) by Day 28
 
Proportion of subjects hospitalized (defined as <math>\geq 24</math> hours) due to COVID-19 related events by Day 28
 
Days of hospitalization due to all causes or COVID-19
 
Proportion of subjects with all-cause mortality by Day 28
 
Proportion of subjects with COVID-19 related mortality by Day 28
 
Proportion of subjects admitted to an ICU due to COVID-19 by Day 28
 
Days in intensive care unit (ICU)
 
Proportion of subjects requiring supplemental oxygen, high-flow oxygen, any ventilation or ECMO due to COVID-19 by Day 28
 
Proportion of subjects requiring mechanical ventilation or ECMO due to COVID-19 by Day 28
 
Days on supplemental oxygen/high flow oxygen devices/mechanical ventilation
 

Characterize the effect of GT0918 compared to placebo on symptom improvement or resolution	
Symptom Improvement:
 
 
Change in symptom score (total of ratings) from baseline to Days 3, 7, 14 and 28
 
Time to symptom improvement
 
Proportion of subjects demonstrating symptom improvement via the symptom questionnaire (total of ratings) on Days 3, 7, 14 and 28
 
 
Symptom resolution:
 
 
Proportion of subjects demonstrating symptom resolution via the symptom questionnaire on Days 3, 7, 14 and 28
 
Time to symptom resolution
 

Characterize the effect of GT0918 compared to placebo on SARS-CoV-2 viral load clearance	
 
Change from baseline to Days 3, 7, 14 and 28 in SARS-CoV-2 viral load
 
Proportion of subjects that achieve SARS-CoV-2 clearance (Days 3, 7, 14 and 28)
 
Time to SARS-CoV-2 clearance
 
SARS-CoV-2 viral load area under the concentration-time curve (AUC) assessed to days 3, 7, 14 and 28
 

Characterize the effect of GT0918 compared to placebo on safety	Safety assessments such as AEs, SAEs and laboratory data
Exploratory	Exploratory
Characterize the pharmacokinetics of GT0918	
 
Mean trough concentration of GT0918 and GT0955 on Days 1, 3, 7 and 14
 
To explore relationships between GT0918 and/or GT0955 exposure and selected efficacy and safety endpoints and/or biomarkers
 

Characterize emergence of viral resistance to GT0918	Screening for novel mutants in patients who do not respond to GT0918 

• Genotype of SARS-CoV-2 viral isolates

To explore biomarkers predictive of GT0918 safety, efficacy, and/or disease progression and COVID-19 clinical outcomes	The association between changes in disease related biomarkers with clinical endpoints

## 4 STUDY DESIGN

### 4.1 Description of Study Design

This is a Phase 3, randomized, double-blind, placebo-controlled, multicenter study to evaluate the safety and efficacy of Proxalutamide (GT0918) in adult outpatients diagnosed with mild to moderate COVID-19. The study will be 2-arm comparison against matched placebo. The study will be conducted in around 100 sites in the USA and other countries.

This study utilizes an adaptive design that maximizes our efficiency in identifying a safe and efficacious therapeutic agent for COVID-19 during the current outbreak. There will be an interim analysis after 334 subjects complete Day 28 after the first dose to allow early stopping for futility, efficacy, or safety.

The study population will be subjects with mild to moderate COVID-19 illness chosen to evaluate if early intervention with anti-androgen therapy prior to respiratory compromise can effectively prevent progression to the severe form of COVID-19 illness.

Randomization is essential for establishing efficacy of these new therapeutic agents.

The blood samples for PK analysis need to be collected for at least 200 subjects, whom will also be randomized into the interventional treatment or placebo group with 1:1 ratio.

### Schema

[figure not shown]

Figure 4: Study GT0918-US-3001 schema.

#### 4.1.1 Screening and Randomization

After signing the study ICF, the screening assessments will be done within 1 day prior to randomization for selected assessments (See SoA) for the list of assessments to be performed).

The investigator will review symptoms, risk factors and other inclusion and exclusion criteria to confirm subject's eligibility.

Subjects will be randomized into 1 of 2 arms with 1:1 ratio, each will receive an interventional treatment/placebo.

Randomization will be stratified by the following factors:

- Sex: Male or Female
- Race and ethnicity (non-Hispanic White or others /Hispanic or Latino /non-Hispanic Black)
- Number of risk factors 0, 1-2,  $\geq 3$  (based on CDC defined conditions <https://www.cdc.gov/coronavirus/2019-ncov/need-extra-precautions/people-with-medical-conditions.html>). Adults with the following conditions are at increased risk of severe illness from the virus that causes COVID-19:
  - Age  $\geq 65$  years
  - Cancer
  - Chronic kidney disease
  - Chronic lung diseases, including COPD (chronic obstructive pulmonary disease) asthma (moderate to severe), interstitial lung disease, cystic fibrosis, and pulmonary hypertension
  - Dementia or other neurological conditions
  - Down Syndrome
  - Heart conditions, such as heart failure, coronary artery disease, or cardiomyopathies or hypertension
  - Immunocompromised state (weakened immune system) from solid organ transplant
  - Liver disease
  - Overweight and Obesity (body mass index [BMI]  $\geq 25$  kg/m^2)
  - Sickle cell disease or thalassemia
  - Smoking, current or former
  - Diabetes Type 1 or type 2)
  - HIV infection
  - Solid organ or blood stem cell transplant
  - Stroke or cerebrovascular disease, which affects blood flow to the brain

- Substance use disorders
- Others per most updated list from CDC website as above

#### **4.1.2 Treatment Duration**

Subject will receive treatment for 14 days, Day 1 to Day 14. From screening visit Day -1 to visit Day  $28 \pm 2$  days post last treatment which corresponds to Day 42 Safety Follow-up visit. The scheduled procedure shown in the [Schedule of activities \(SoA\)](#)

#### **4.2 Timing of Interim Analyses and Design Adaptations**

The ongoing study may be modified based on planned interim analyses. Based on the observed data at the time of the interim analyses, the study may:

- suspend enrollment to GT0918 treatment arm demonstrating lack of efficacy, and/or
- initiate/expand enrollment to the existing GT0918 treatment arm

The modifications proposed are done so to ensure subjects are being exposed to treatment with an acceptable risk-benefit profile during the ongoing study. Additionally, the potential modifications will provide information to characterize the dose response profile more fully.

Monitoring of unblinded safety data (including AEs, SAEs, and selected laboratory measurements) will occur throughout the study and will be conducted by IDMC members.

#### **4.3 End of the study**

A subject is considered to have completed the study if he has completed all required phases of the study including the last scheduled procedure shown in the SoA.

The end of the study is defined as the date of last scheduled procedure shown in the SoA for the last enrolled subject or last ongoing subject in the study, whichever comes later.

#### **4.4 Early Study Termination**

The study can be terminated at any time for any reason by Kintor. Should this occur, the subject should be seen as soon as possible and the same assessments should be performed as described in Section 7 for a discontinued or withdrawn subjects. The investigator may be informed of additional procedures to be followed in order to ensure that adequate consideration is given to the protection of the subject's interest. The investigator will be responsible for informing IRBs and/or ECs of the early termination of the trial.

## 5 POPULATION

### 5.1 Patient Population

The target population of this study are those adult subjects with mild to moderate COVID-19 illness with first positive SARS-CoV-2 virus test within 3 days, to evaluate if anti-androgen therapy may effectively prevent progression to the severe form of COVID-19 illness by treating this population early in their disease course and prior to respiratory compromise and failure. This study plans to have around 668 subjects in the US or may expand to other countries/regions for GT0918 and the placebo groups, the randomization rate is 1:1.

### 5.2 Inclusion Criteria

Subjects are eligible to be included in the study only if all the following criteria apply:

1. The subject or legally authorized representative give signed informed consent which includes compliance with the requirements and restrictions listed in the ICF and in this protocol.
2. Understand and agree to comply with planned study procedures.
3. Male and non-pregnant female subjects with age  $\geq 18$  years of age at the time of randomization.
4. Are currently not hospitalized.
5. Have one or more COVID-19-related symptoms within 5 days of symptoms onset ((FDA COVID-19-Related symptom guidance, See Appendix 2, available at: <https://www.fda.gov/media/142143/download>)
6. Must have first positive SARS-CoV-2 viral infection determination (has laboratory-confirmed SARS-CoV-2 infection as determined by PCR, or other commercial or public health assay in any specimen)  $\leq 3$  days prior to start of the first dose.
7. Women of child-bearing potential, defined as all women physiologically capable of becoming pregnant, unless they are using highly effective contraception, as shown below, throughout the study and for 3 months after stopping GT0918 treatment. Highly effective contraception methods include:
  - Total Abstinence (when this is in line with the preferred and usual lifestyle of the patient. Periodic abstinence (e.g. calendar, ovulation, symptothermal, post-ovulation methods) and withdrawal are not acceptable methods of contraception, or
  - Use of one of the following combinations (a+b or a+c or b+c):
    - a: Use of oral, injected or implanted hormonal methods of contraception or other forms of hormonal contraception that have comparable efficacy (failure rate  $< 1\%$ ), for example hormone vaginal ring or transdermal hormone contraception.
    - b: Placement of an intrauterine device (IUD) or intrauterine system (IUS);
    - c: Barrier methods of contraception: Condom or Occlusive cap (diaphragm or cervical/vault caps) with spermicidal foam/gel/film/cream/vaginal suppository;

- Female sterilization (have had prior surgical bilateral oophorectomy with or without hysterectomy) or tubal ligation at least six weeks before taking study treatment. In case of oophorectomy alone, only when the reproductive status of the woman has been confirmed by follow-up hormone level assessment;
- Male sterilization (at least 6 months prior to screening). For female subjects on the study, the vasectomized male partner should be the sole partner for that subject; In case of use of oral contraception women should have been stable for a minimum of 3 months before taking study treatment. Women are considered post-menopausal and not of childbearing potential if they have had 12 months of natural (spontaneous) amenorrhea with an appropriate clinical profile (e.g. age appropriate, history of vasomotor symptoms) or have had surgical bilateral oophorectomy (with or without hysterectomy) or tubal ligation at least six weeks ago. In the case of oophorectomy alone, only when the reproductive status of the woman has been confirmed by follow up hormone level assessment, is she considered not of childbearing potential

8. Regardless of their fertility status, male subjects must agree to either remain abstinent (if this is their preferred and usual lifestyle) or use condoms as well as one additional highly effective method of contraception (less than 1% failure rate) or effective method of contraception with nonpregnant women of childbearing potential partners for the duration of the study and until 90 days after the last dose.
9. Agree to the collection of nasopharyngeal swabs and venous blood.

### 5.3 Exclusion Criteria

Subjects are excluded from the study if any of the following criteria apply:

1. Have  $\text{SpO}_2 \leq 93\%$  on room air at sea level or  $\text{PaO}_2/\text{FiO}_2 < 300$ , respiratory rate  $\geq 30$  per minute, heart rate  $\geq 125$  per minute (FDA resource page, <https://www.fda.gov/media/137926/download>)
2. Estimated glomerular filtration rate (eGFR)  $< 30$  ml/min
3. Serum total bilirubin  $> 1.5 \times \text{ULN}$  (upper limit of normal) and AST and ALT  $> 3 \times \text{ULN}$
4. Subjects with significant cardiovascular disease as following:
  - i. heart failure NYHA class  $\geq 3$
  - ii. left ventricular ejection fraction  $< 50\%$
  - iii. those with a history of cardiac arrhythmias, including long QT syndrome.
5. Has been admitted to a hospital prior to randomization, or is hospitalized (inpatient) at randomization, due to COVID-19 or requires treatment with supplemental oxygen.
6. Have known allergies to any of the components used in the formulation of the interventions.
7. Have hemodynamic instability requiring use of vasopressors within 24 hours of randomization.
8. Suspected or proven serious, active bacterial, fungal, viral, or other infection (except COVID-19) that in the opinion of the investigator could constitute a risk when taking intervention (i.e. known history of human immunodeficiency virus [HIV]).

---

9. Have any co-morbidity requiring surgery within <7 days, or that is considered life-threatening within 30 days.
10. Have any serious concomitant systemic disease, condition, or disorder that, in the opinion of the investigator, should preclude participation in this study.
11. Subjects with myopathy
12. Prior, current, or planned future use of any of the following treatments: COVID-19 convalescent plasma, mAbs against SARS-CoV-2, IVIG (any indication), where prior use is defined as the past 30 days or less than 5 half-lives of the investigational product (which is longer) from screening.
13. Have participated, within the last 30 days before dosing, in a clinical study involving an investigational intervention. If the previous investigational intervention has a long half-life, 5 half-lives or 30 days, whichever is longer, should have passed.
14. Are concurrently enrolled in any other type of medical research judged not to be scientifically or medically compatible with this study.
15. Subject taking or had taken an anti-androgen of any type including androgen deprivation therapy, 5-alpha reductase inhibitors, etc. within 3 months before dosing.
16. Are investigator site personnel directly affiliated with this study.

## 6 TREATMENT

### 6.1 Study Treatment

For this study, study treatment in this study refers to GT0918 in the treatment arm and placebo in the placebo arm. GT0918 will be supplied by Kintor or its designee as 100 mg tablets as individual patient supply packaged in blister. All dosages prescribed and dispensed to the patient and all dose changes during the study must be recorded on the Dosage Administration Record eCRF.

#### 6.1.1 Dosing Regimen

Eligible subjects will be randomized before or on Day 1 to receive either GT0918 or matched placebo. GT0918/placebo will be given 200mg orally once daily on Days 1-14 during the study period. Days 15-28 will be the post-treatment period without dosing with GT0918/placebo.

The study drug will be administered as a flat-fixed dose and not by body weight or body surface area. The dose should be given the same time each day (+/- 2 hours for medication scheduling) around 30 minutes after meal for consecutive 14 days. During screening visit (D-1) or D1, after confirmation of subject's eligibility, the drugs or placebo as well as Subject Diary with Questionnaire will be provided to subjects. The subject will document the dose date/time with the Diary and answer the Questionnaire daily.

The study treatment period is shown as below.

## Timeline

**Figure 5. Overview of study period and group assignment**

The investigator or responsible personnel will instruct the subject to take the study drugs as per-protocol. Subjects will be instructed to return unused study drugs (if applicable) to the sites at discontinuation or completion of treatment. The site personnel will ensure that appropriate dose of each study drug is administered, and that drug accountability is performed.

### 6.1.1.1 General Dosing Guidelines

The study treatments should be taken as follows:

- Subjects should be instructed to take the study treatment of GT0918/placebo two tablets together with a glass of water once a day at the same time each day.
- In general, study treatment may be taken after normal conventional meal ( $\pm 2$  hours for medication scheduling).
- Subjects will be instructed to swallow the tablets whole and not to chew or crush them.
- If vomiting occurs, during the course of treatment, no re-dosing of the drug is allowed before the next scheduled dose. The occurrence and frequency of any vomiting during the treatment period must be noted in the AEs section of the eCRF. Missing dose should be documented at Subject Diary.
- Any doses that are missed should be skipped and should not be replaced or made up on a subsequent day.
- Subjects try to avoid consumption of grapefruit, grapefruit hybrids, pomelos, starfruit, Seville oranges or products containing their juice during the treatment period. These foods are known as CYP3A4 inhibitors and have a potential to increase exposure to GT0918. Orange juice is allowed.
- Multivitamins are permitted.

### 6.1.2 Guidelines for Continuation of Treatment

The treatment course continues as described above even if the subject becomes SARS-CoV-2 test negative.

### **6.1.3 Ancillary Treatments**

This section is not applicable for this study.

### **6.1.4 Rescue Medication**

This section is not applicable for this study.

### **6.1.5 Treatment Duration**

The treatment period starts from Day 1 (first oral administration of drug or placebo) to D14, 14 consecutive days.

## **6.2 Dose Escalation**

This section is not applicable for this study. No dose escalation or de-escalation is allowed through the whole study.

## **6.3 Dose Modifications**

### **6.3.1 Dose Discontinuation**

Any subject who develops  $\geq$  Grade 3 treatment emergent adverse events that are possibly, probably or definitely related to the study drug as assessed by the investigator will discontinue the treatment. There is no dose interruption or dose reduction in this study.

The treatment course should be continued if the subject becomes SARS-CoV-2 test negative or experiences complete resolution of symptoms.

For the subjects who are hospitalized during the study, the subject may continue the study treatment at the investigator's discretion based on individual benefit/risk assessment.

### **6.3.2 Follow-Up for Toxicities**

Subjects, whose treatment is permanently discontinued due to an AE must be followed up at least twice a week if applicable (or more frequently if required by institutional practices, or if clinically indicated) for 4 weeks or until resolution or stabilization of the event, whichever comes first. Appropriate clinical experts should be consulted as deemed necessary.

All AEs/SAEs will be followed until resolution, stabilization, the event is otherwise explained, or the subject is lost to follow-up ([Section 7.1.6](#)). Further information on follow-up procedures is provided in [Section 8.1](#).

### **6.3.3 Anticipated Risks and Safety Concerns of the Study Treatment**

Appropriate eligibility criteria and stopping rules are included in this protocol. Recommended guideline for supportive treatment for expected toxicities, including management of study drug induced AEs are provided in [Section 6.3.2](#). More anticipated risks and safety concerns, reference of preclinical toxicity and clinical data are in the IB.

## 6.4 Concomitant Medications

In general, the use of any concomitant medication/therapy deemed necessary for the care of the subject is permitted, except when specifically prohibited.

The subject must be told to notify the investigational site about any new medication he takes after the start of study treatment. All medications, including herbal/natural medications (excluding study treatment), surgeries, and procedures (including physical therapy) administered within 30 days prior to the first dose of administration of study treatment through 28 days after the last dose of administration study treatment will be recorded in the concomitant medications or surgical and medical procedures eCRF, respectively.

### 6.4.1 Permitted Concomitant Therapy

#### Prior Treatment for Indication

Any prior therapy, such as antivirals, antibiotics, or antimalarials used as treatment prior to signing informed consent should be recorded.

Therapy prior to enrollment with antivirals including lopinavir/ritonavir, remdesivir, or other therapeutic agents (e.g., corticosteroids) are permitted.

#### Concomitant Therapy During the Study

Subjects should be treated according to standard of care, even as it evolves, and medications may be part of the treatment paradigm.

Therefore, remdesivir may be initiated as standard of care for subjects hospitalized with severe disease (if available through the FDA Emergency Use Authorizations) outside of local standard of care per written policies or guidelines.

If the local standard of care per written policies or guidelines (that is, not just an individual clinician decision) includes lopinavir/ritonavir, chloroquine, hydroxychloroquine or other investigational agents, then initiating these during the study is permitted, but may require additional safety monitoring by the site.

Acetaminophen and corticosteroid use are permitted during the study per investigator's discretion.

Other concomitant medication may be considered on a case-by-case basis by the investigator in consultation with the Sponsor if required.

Any medication, including not only physician prescribed medications, but also all over-the counter (OTC) medications, herbal medications, vitamin supplements, blood transfusion or others that the subject is receiving at the time of enrollment or during the study must be recorded along with:

- Reason for use including standard of care for COVID-19.
- Dates of administration including start and end dates.
- Dosage information including dose and frequency for concomitant therapy.

---

The Sponsor should be contacted if there are any questions regarding concomitant or prior therapy.

#### **6.4.2 Prohibited Concomitant Therapy**

Strong CYP3A enzyme inhibitors and inducers and P-gp transporter inhibitors and inducers are prohibited.

Any medicine or treatment may influence evaluation of efficacy of study drug is prohibited, Spironolactone, anti-androgen drug or treatment including but not limited to 5 $\alpha$ -Reductase Inhibitors, androgen deprivation therapy, Enzalutamide, Bicalutamide, Abiraterone. Or Cycloprogesterone, Androgen, Estrogen or AR antagonists.

Convalescent COVID-19 plasma treatment is not allowed. The monoclonal antibody therapy Bamlanivimab alone, or Casirivimab and Imedevimab in combination under the EUA for the treatment of mild to moderate COVID-19 patients is prohibited in this study.

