### **2.4 Rationale for Choice of Comparator Drugs**

Subjects enrolled in this study will either be mild or moderate COVID-19 who are not hospitalized. There are no approved treatment options for this patient population except an EUA for the investigational monoclonal antibody therapy. Bamlanivimab alone or Casirivimab and Imedevimab given together or Bamlanivimab and etesevimab given in combination for the treatment of mild-to-moderate COVID-19 in adult and pediatric patients. Therefore, placebo comparator was selected, however, best supportive therapy/standard of care except those are prohibited in Section 6.4.2 can be administered in both treatment and control groups as required at the investigator's discretion.

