#### **6.4.3 Concomitant Therapy to Be Used with Caution**

Concomitant treatment of GT0918 with weak inhibitors or inducers of CYP3A4 is permitted. Caution is advised when GT0918 is co-administered with drugs that are moderate/strong inhibitors or inducers of CYP3A4. Duration of concomitant treatment should be kept as short as possible, or completely avoided whenever possible. Subjects receiving such medications must be monitored closely for any potential toxicity or decreased clinical benefit due to any individual concomitant medications.

Concomitant treatment of GT0918 with medications which have narrow therapeutic index/sensitive substrates for CYP3A4/2D6 is allowed with caution. Detailed lists of inhibitor, substrates and inducers of CYP3A or pertinent medicines are listed to Appendix 1.

Any narrow therapeutic index/sensitive CYP 3A, or 2D6, or both substrate drug(s) should be excluded from patient use if possible, then switch to a suitable alternative drug(s). If no suitable alternatives are available, it is recommended to reduce the dose of the narrow therapeutic index/sensitive CYP 3A, or 2D6, or the substrate drug(s).

Inducers or nutritional supplement of cytochrome P450 3A4, such as St. John's Wort Extract grapefruit, and immunosuppression medicine are needed to be used with caution.

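### Protocol 6.4.2 bans strong CYP3A inhibitors and inducers outright, while 6.4.3 lets them be given with caution and monitoring

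*Protocol*

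**What the plan says.** Protocol 6.4.2 contains the ban: "Strong CYP3A enzyme inhibitors and inducers and P-gp transporter inhibitors and inducers are prohibited". It names no exception.

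Protocol 6.4.3 covers part of the same class under caution: "Caution is advised when GT0918 is co-administered with drugs that are moderate/strong inhibitors or inducers of CYP3A4". It goes on: "Duration of concomitant treatment should be kept as short as possible, or completely avoided whenever possible". It then requires that "Subjects receiving such medications must be monitored closely for any potential toxicity or decreased clinical benefit". It also says that St. John's "Wort Extract grapefruit, and immunosuppression medicine are needed to be used with caution". For the drugs concerned it points to Appendix 1, whose title presents them as drugs to be used cautiously. That table has separate columns for strong CYP3A4 inhibitors and strong CYP3A inducers. Lopinavir with ritonavir and grapefruit juice are in the first, St. John's wort in the second.

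Protocol 6.4.1 lets a site start lopinavir/ritonavir during the study if written local policy or guidelines make it standard of care, possibly with extra safety monitoring. On treatment before enrollment it says: "Therapy prior to enrollment with antivirals including lopinavir/ritonavir, remdesivir, or other therapeutic agents (e.g., corticosteroids) are permitted". SAP 4.7 names lopinavir/ritonavir among the standard-of-care drugs to be summarized separately.

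Two general statements bear on which section wins. Protocol 2.4 says that "best supportive therapy/standard of care except those are prohibited in Section 6.4.2 can be administered in both treatment and control groups". Protocol 6.4 says that "the use of any concomitant medication/therapy deemed necessary for the care of the subject is permitted, except when specifically prohibited".

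**The concern.** A monitoring rule for subjects who receive strong modulators presupposes use that another section forbids. Two sites with the same subject could decide differently, each citing the protocol, on whether the drug may be given and whether giving it is a deviation.

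The protocol gives its own reasons to care. Section 1.2.2.4 reports, from human liver microsomes, that CYP3A4 is the main enzyme forming the major metabolites of GT0918. Section 6.1.1.1 warns that foods inhibiting CYP3A4 may raise exposure. Section 6.4.3 names both toxicity and loss of benefit. The exclusion criteria in 5.3 contain nothing on CYP3A modulators, so section 6.4 is the only control. A subject already taking a listed strong inducer such as carbamazepine or phenytoin could enroll, and the site would meet the contradiction on Day 1. Section 6.3.1 allows neither interruption nor reduction of dose.

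On the analysis side, SAP 4.5 builds the per-protocol set from mITT subjects without major violations, and SAP 4.10.2 uses that set for a sensitivity analysis. An unclear rule on prohibited drugs could therefore affect who is in it.

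**Working it through.** There is no figure in the plan to reproduce. The check sets the texts side by side, with one small count.

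| Place | Strong CYP3A agents as a class | St. John's wort | Lopinavir/ritonavir | Grapefruit |
|---|---|---|---|---|
| Protocol 6.4.2 | banned, no exception | banned if strong | banned if strong | banned if strong |
| Protocol 6.4.3 | caution, short use, monitoring | caution | within the class caution | caution |
| Protocol Appendix 1 | own columns, under a caution title | strong inducer | strong inhibitor | strong inhibitor (juice) |
| Protocol 6.4.1 | not addressed | not addressed | may be started if in written local policy | not addressed |
| Protocol 6.1.1.1 | not addressed | not addressed | not addressed | subjects try to avoid it |
| SAP 4.7 | not addressed | not addressed | summarized as standard of care | not addressed |

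**Step 1: can 6.4.2 and 6.4.3 both be obeyed?** Yes, if the site never gives a strong agent, since 6.4.3 also prefers avoidance. Once one is given, they part: prohibited use under 6.4.2, monitored use under 6.4.3. The different labels, CYP3A in one and CYP3A4 in the other, do not reconcile them, because Appendix 1 uses both.

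**Step 2: is Appendix 1 a separate contradiction?** Only weakly. Section 6.4.3 cites it as a list of inhibitors, substrates and inducers. It includes enzalutamide, which 6.4.2 bans by name, so its title cannot be permission for every entry. It works mainly as a classification table with a misleading title.

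**Step 3: is 6.4.1 a separate contradiction?** Partly. The permission is for standard of care only, and 2.4 makes standard of care subject to 6.4.2. Ambiguity remains because 6.4.1 names a drug that Appendix 1 calls strong and 6.4.2 carves out nothing. It also does not say whether lopinavir/ritonavir begun before enrollment must stop.

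**Step 4: what experience exists above the 200 mg dose?** From the completed oncology studies in Protocol 1.2.3.1.1:

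- GT0918-US-1001: 300 mg, 7; 400 mg, 7; 500 mg, 6; 600 mg, 5. Sum: 7 + 7 + 6 + 5 = 25.
- GT0918-CN-1001: 300 mg, 3; 400 mg, 4. Sum: 3 + 4 = 7.
- GT0918-CN-1003: 300 mg, 36.
- Total: 25 + 7 + 36 = 68 subjects. The highest dose was 600/200 = 3 times this trial's dose.

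The two phase 1 studies report no dose-limiting toxicity. In GT0918-US-1001 a Grade 4 creatine phosphokinase increase is the stated exception to the serious and Grade 3 or higher events being unrelated to drug. This is a margin in dose. Without interaction data it cannot be turned into a margin in exposure, and it says nothing about inducers, where the worry is too little drug.

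**The case against.** The strongest reply is that the protocol already contains a precedence rule. Section 2.4 subjects standard of care to 6.4.2, and 6.4 permits other drugs only when they are not specifically prohibited. Section 6.4.1 also sends questions on concomitant therapy to the sponsor. A cautious site that avoids every strong modulator breaches nothing. This stands as evidence of intent and answers most of the lopinavir/ritonavir item. It does not change the text of 6.4.3, which still tells a site how to manage a subject who is receiving a banned drug.

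It can also be said that safety is protected in other ways: 6.3.1 requires study drug to stop for related events of Grade 3 or higher, and 7.1.3.1 tells investigators to stop treatment they judge detrimental. That stands too. These measures act after harm appears, and neither would detect exposure lost to an inducer.

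A reader might infer more than the documents support:

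- *That the conflict is large because Appendix 1 has many strong entries.* There are 22 inhibitors + 7 inducers = 29, but they repeat one conflict and do not measure its size.
- *That the efficacy result or the per-protocol set is compromised.* The mITT set in SAP 4.5 does not depend on concomitant drugs. Major deviations are defined in a Protocol Deviation Specification (SAP 4.4.2) that is not among these documents, so an effect on the per-protocol set can be neither shown nor ruled out.
- *That subjects were exposed to a harmful interaction.* No interaction data with strong modulators and no count of users are given.

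**Conclusion.** The point holds as a contradictory conduct and safety rule, wrong as written, of low to moderate severity. The firm part is 6.4.2 against 6.4.3, including St. John's wort. The Appendix 1 title and the conditional permission in 6.4.1 are secondary ambiguities.

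The size of any exposure change and the number of subjects affected are unknown. Sample size, alpha, power and the primary mITT analysis are untouched.

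The conclusion assumes that Appendix 1's strong labels apply as printed. The footnote letters beside several entries, including St. John's wort and lopinavir/ritonavir, have no text in the copy read, so a qualification there could alter individual drugs. It would not remove the clash over the class as a whole.

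**What to change.** 1. In 6.4.3, change *moderate/strong* to *moderate* and remove St. John's wort, which then falls under 6.4.2 as a strong inducer per Appendix 1.
2. Retitle Appendix 1 and mark its strong CYP3A columns as prohibited under 6.4.2.
3. In 6.4.1, make the lopinavir/ritonavir permission subject to 6.4.2 while study drug is being taken, and say that this includes a course begun before enrollment. If the sponsor wants to keep the permission, write it into 6.4.2 as an explicit exception with monitoring. Align SAP 4.7 with whichever is chosen.
4. If grapefruit juice is to stay under dietary advice, write that exception into 6.4.2.
5. Confine any time limit tied to dosing to the CYP3A drugs. The bans on antibodies, convalescent plasma and anti-androgens should stay as they are; the primary endpoint runs to Day 28, beyond the 14 days of dosing.
6. Apply the same rule in the Protocol Deviation Specification before database lock. If dosing has already ended, this and the SAP 4.7 alignment are the parts that still matter.

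The cost is wording in four places of the protocol (6.4.1, 6.4.2, 6.4.3 and Appendix 1) and one in the SAP, with a clarification to sites. The downside is that some subjects, in unknown number, may have to forgo these drugs during dosing.
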